## **7 SAFETY EVALUATION**

### **7.1 Safety parameters**

The safety parameters that are measured at every study visit are shown in Table 2. The investigator will collect required data including:

- 1) documentation of significant medical history at the screening visit the following visits,
- 2) identification and documentation of adverse events, including abnormalities identified with:
  - a) physical examination,
  - b) laboratory tests.

The investigator will collect and interpret all relevant information and make a decision on whether to report any deviation from the norm, as an adverse event.

### **7.2 Methods and timing**

Methods and timing of the parameters identification are as follows:

**Physical examination.** During the patient screening and enrollment and at the final visit, the investigator will document the patient's complaints and abnormalities, detected on

physical examination. All clinically significant abnormalities should be reported as adverse events.

**Blood pressure and heart rate.** All patients will have their blood pressure and heart rate measured at every visit. If blood pressure and heart rate are abnormal, the investigator will evaluate the clinical significance of the abnormality and decide on whether to document it as an adverse event.

**Laboratory tests parameters:** creatinine (including creatinine clearance calculation according to Cockcroft-Gault equation), potassium, sodium, ALT, AST. Fasting blood samples will be obtained at screening and at the final visit. Results of the tests will be entered into the CRF. If the sample is lost, the investigator may order resampling if medically indicated (e.g., if invalid test results are suspected).

All clinically significant adverse deviations from the baseline (screening) will be reported as adverse events.

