### **Treatment regimens**

- **Group 1** patients receive moxonidine with dose titration up to the maximum, then a patient may be switched to the combination therapy, if necessary (step 2 - adding an ACE inhibitor).
- **Group 2** patients receive bisoprolol with dose titration up to the maximum, then a patient may be switched to the combination therapy, if necessary (step 2 - adding an ACE inhibitor).

The investigator will provide a Group 1 patient with moxonidine 0.4 mg in the amount required for 56 days of treatment plus 7 extra days and additionally moxonidine 0.2 mg in an amount required for 42 days of treatment if the dose is titrated up to 0.6 mg/day.

The patient will take the first moxonidine tablet immediately during the visit after all the visit procedures are completed. The patient will be instructed to take 1 tablet of moxonidine 0.4 mg in the morning, daily. The next visit will be scheduled in week 8 after the enrollment visit (in 56 days  $\pm$  5 days after the enrollment visit).

The patient will be asked to bring all the blisters of investigated product (empty, started and not started blisters) to every visit after the study initiation.

The investigator will give the patient blood pressure self-monitoring diary which is to be used by the patient to daily document her BP values and to bring it to every subsequent visit.

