## 8 ADVERSE EVENTS

### Definitions

#### 8.1 Adverse event (AE)

Any untoward medical occurrence in a patient or clinical investigation subject administered a pharmaceutical product, including laboratory parameters deviations. AE does not necessarily have a causal relationship with the treatment.

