#### **10.4 Safety analysis**

All safety data will be analyzed in the safety analysis population. Safety analysis includes identification of all adverse events, including serious adverse events at every visit following the screening.

Analysis of adverse events including serious adverse events will be conducted to determine the total number of AEs, the total number of patients with adverse events, the number of treatment-related adverse events, the number of AEs associated with product discontinuation and the number of voluntary withdrawal of informed consent.

Rate and severity of all adverse events and drug-related adverse events (i.e., at least “possibly” associated with the studied product) will be summarized by organ systems. Data on the product withdrawal due to adverse events will be summarized in tables. The safety results will be presented using descriptive statistics.

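### Section 7.2 reports clinically significant examination abnormalities as adverse events without requiring them to be new or worse than before dosing, so pre-existing findings at V1 or V4 can enter the all-cause adverse event tables

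*Combined protocol and SAP*

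**What the plan says.** All references are to the combined protocol and SAP.

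- **7.2, Physical examination.** The timing is: "During the patient screening and enrollment and at the final visit, the investigator will document the patient's complaints and abnormalities". The reporting rule that follows is: "All clinically significant abnormalities should be reported as adverse events". No comparison with an earlier examination is mentioned.
- **7.2, Laboratory tests.** Here a comparison is required: "All clinically significant adverse deviations from the baseline (screening) will be reported as adverse events".
- **7.1.** The investigator is to interpret the information and "make a decision on whether to report any deviation from the norm, as an adverse event".
- **8.1.** An adverse event is "Any untoward medical occurrence in a patient or clinical investigation subject administered a pharmaceutical product, including laboratory parameters deviations". Onset or worsening after the first dose is not part of the definition.
- **3.6.2 (V1).** The visit text asks for adverse events linked to protocol procedures since consent. On dosing, the Treatment regimens text says: "The patient will take the first moxonidine tablet immediately during the visit after all the visit procedures are completed".
- **3.6.6 (V4).** A full physical examination is not required.
- **10.4.** The safety analysis covers "identification of all adverse events, including serious adverse events at every visit following the screening". The outputs include the total number of events, the number of patients with events, and rates by organ system, with drug-related events also summarised. All are descriptive.

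**The concern.** A comparative adverse event table is meant to show what happened after treatment began. Under the examination rule in 7.2, a long-standing abnormality that an investigator judges clinically significant is an adverse event if seen at V1 before any tablet is taken, and again an adverse event if it is unchanged at V4. The laboratory rule in the same section shows that a baseline comparison was in mind for one type of finding and was not carried over to the other.

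At stake is the meaning of the all-cause tables. Pre-existing findings would raise the apparent event rate of both drugs and make the two arms look more alike on the proportion of patients with an event. In addition, whether a stable abnormality counts depends on which section a site follows, so sites and investigators may not record alike.

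**Working it through.** **Step 1: can pre-dose findings reach the tables?**

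- Screening (V0): 7.2 names this visit, but 10.4 analyses visits after screening. V0 findings should not be counted.
- Enrolment (V1): 7.2 names it and 10.4 includes it. Section 3.1 has baseline data collected before randomisation in both arms, and 3.6.2 puts the first moxonidine tablet after all visit procedures. An abnormality found at the V1 examination is therefore pre-dose.
- Final visit (V4): 7.2 names it and 10.4 includes it. An unchanged abnormality meets the 7.2 rule if it is looked for, but 3.6.6 does not require a full examination.
- Possible repair elsewhere: none found. No treatment-emergent definition appears. Section 10.4 refers to a safety population, but the populations listed after 10.2 are only ITT and PP.

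The route exists at V1 and V4 and not at V0. Because 3.6.2, 7.1 and 3.6.6 pull the other way, entry is possible rather than certain.

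**Step 2: effect on the proportion of patients with an event.** The documents give no adverse event rates, so there is no figure of the plan's own to reproduce and every rate below is an assumption. Let r be the true on-treatment proportion in an arm and p the share of women with a counted pre-existing finding, equal in both arms and independent of on-treatment events.

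Observed proportion = p + (1 - p) × r

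Observed difference = (1 - p) × (r1 - r2)

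With r1 = 30% and r2 = 15% (a true difference of 15 points):

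| p | Arm 1 | Arm 2 | Difference |
|---|---|---|---|
| 0% | 30% | 15% | 15 points |
| 5% | 0.05 + 0.95 × 0.30 = 33.5% | 0.05 + 0.95 × 0.15 = 19.25% | 14.25 points |
| 20% | 0.20 + 0.80 × 0.30 = 44% | 0.20 + 0.80 × 0.15 = 32% | 12 points |
| 40% | 0.40 + 0.60 × 0.30 = 58% | 0.40 + 0.60 × 0.15 = 49% | 9 points |

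**Step 3: effect on total event counts.** Assume Poisson means of 0.5 and 1.0 events per patient, 57 women per arm (section 3.2), and a common background of m pre-existing findings per patient.

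Difference = (1.0 + m) - (0.5 + m) = 0.5 for any m

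Standard error = √((0.5 + 1.0 + 2m) / 57)

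- m = 0: √(1.5 / 57) = 0.162; ratio 1.0 / 0.5 = 2.00.
- m = 1: √(3.5 / 57) = 0.248; ratio 2.0 / 1.5 = 1.33.

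The absolute difference in counts keeps its expected value and becomes noisier. The ratio moves towards 1.

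**The case against.** The strongest reply is that other text already limits what is recorded. At V1, 3.6.2 asks only for procedure-related events. At V2 to V4, sections 3.6.4 to 3.6.6 ask for the history since the previous visit, which suggests new occurrences. V4 needs no full examination. Medical history and comorbidities have their own channel at screening. Section 7.1 leaves the decision to the investigator, and a stable old condition is not naturally an occurrence in a treated subject under 8.1. The exclusion criteria remove many conditions likely to give significant findings, so p may be small.

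This stands in part. It makes the inflation possible rather than certain, and it is why a value as low as 5% belongs in the range. It does not remove the problem: 7.2 states its rule without exception, nothing says which section prevails, and a site following 7.2 to the letter would be compliant.

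Three stronger readings are tempting, and the documents do not support them:

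- A reader might infer that every complaint becomes an adverse event. Section 7.2 has complaints documented, but its reporting sentence names abnormalities only.
- A reader might infer that screening findings inflate the counts. Section 10.4 starts after screening.
- A reader might infer that every safety contrast is diluted. Step 3 shows that the absolute difference in counts is not. The drug-related summary should screen out most pre-existing findings, because even a possible relationship requires a reasonable time sequence to dosing.

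**Conclusion.** The point holds in a limited form. The examination rule in 7.2 lacks a new-or-worse condition, differs from the laboratory rule beside it, and does not fit 3.6.2, 7.1 or 3.6.6. Pre-existing abnormalities recorded at V1, or still present at V4, can therefore enter the all-cause adverse event tables.

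If they do, each arm's rate is overstated and the difference in the proportion of patients with an event shrinks by (1 - p). For an assumed 15-point difference the loss is 0.75 points at p = 5%, 3 at 20% and 6 at 40%. These sizes rest on assumed rates, an unknown p, equal background in the two arms, and independence of background and on-treatment events. Equal background is expected for V1 findings, which precede randomisation. It is less secure at V4, because the trial is open-label and the investigator knows the arm when judging an old finding.

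No planned hypothesis test is put at risk: safety is descriptive and is not among the listed objectives or endpoints. The harm is to how the all-cause tables read, and that is enough to justify a wording change.

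**What to change.** - **7.2.** Record examination abnormalities present at V0, or at V1 before the first dose, as medical history or baseline findings. Report as adverse events only those that are new or worse than at the pre-dose examination.
- **7.1 and 8.1.** Align both with the same new-or-worse rule, so that a stable abnormality is classified the same way whichever section is read.
- **10.4.** Base by-arm adverse event counts on onset or worsening after the first dose. List the pre-dose procedure-related events requested in 3.6.2 separately.
- **7.2 and 3.6.6.** Reconcile the final-visit examination that 7.2 relies on with the statement that a full examination is not required at V4.

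The cost is small: wording changes and no new data. Reported adverse event totals will be lower, and investigators must compare each finding with the pre-dose examination.

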### **3.6.5 Visit 3 (V3)**

The investigator will document the disease history since the last visit, including all adverse events, changes in concomitant treatment, changes in concomitant medications doses, if any.

The investigator will analyze the effectiveness of the therapy according to the patient's BP self-monitoring diary data.

The investigator measures BP and HR according to the ESH/ESC recommendations that are listed in Appendix 1. Blood pressure and heart rate are measured in a sitting position after 5 minutes of rest. **Two** measurements are done, the average value of the measurements is documented. BP is measured on the same arm during the entire study.

Fasting blood sampling will be carried out for the following tests: BMP (potassium, sodium, creatinine, total calcium, inorganic phosphorus, ALT, AST), hormonal test (PTH) and bone metabolism tests, including osteocalcin, Ctx, OPG, RANKL.

The investigator evaluates response to the treatment (target BP reaching), documents it in source documents and decides on further treatment of the patient. If target BP has not been reached, the patient's investigated product dose is titrated according to the study design. If the target BP has been reached, the patient continues with the current treatment until the next visit.

The investigator analyzes the patient's compliance based on the number of returned tablets. The investigator will provide the patient with the investigated medications and invite the patient to the next visit (visit V4) scheduled for week 48 after the enrollment visit (336 days  $\pm$  5 days after the enrollment visit); the patient will be asked to return the investigated medication blisters (empty, started and not started blisters). The patient will be instructed to start taking the provided product the next day morning, 1 tablet per day. The patient will be instructed to report any adverse events (if applicable) to the investigator.

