### **3.6.6 Final visit (V4)**

The investigator will document the disease history since the last visit, including all adverse events, changes in concomitant treatment, changes in concomitant medications doses, if any.

The investigator will analyze the effectiveness of the therapy according to the patient's BP self-monitoring diary data.

The investigator measures BP and HR according to the ESH/ESC recommendations that are listed in Appendix 1. Blood pressure and heart rate are measured in a sitting position after 5 minutes of rest. Two measurements are done; the average value of the measurements is documented. BP is measured on the same arm during the entire study. Full physical examination is not required.

Patient's biochemical blood analysis (total calcium, inorganic phosphorus) is performed. Blood is sampled to investigate bone metabolism: osteocalcin, Ctx, OPG, RANKL.

Blood is sampled to determine telomerase activity.

Dual energy X-ray absorptiometry to determine BMD and detect osteopenia is performed.

Applanation tonometry method is used to measure changes in patient's PWV; duplex ultrasonography of extracranial brachiocephalic arteries is employed to evaluate IMT and subclinical atherosclerosis.

The investigator evaluates the response to the treatment (target BP reaching) and documents it in the source documents, as well as estimates patient compliance based on amount of the returned investigated product.

After successful completion of visit V4 procedures, the patient completes her participation in the study. The investigated product is discontinued; further treatment is carried out according to the attending physician advice.

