**Table 2. Method and frequency of laboratory testing**

Test	Parameters	Laboratory	Method	Frequency
Blood biochemistry	Creatinine* Potassium Sodium ALT AST Total calcium Inorganic phosphorus	Site	Adopted at the hospital center	2x: visits V0 and V3
Blood biochemistry	Total calcium Inorganic phosphorus	Site	Adopted at the hospital center	3x: visits V0, and V3, V4
Hormonal blood test	Parathyroid hormone	Site	Adopted at the hospital center	1x: visit V1
Bone metabolism	Osteocalcin Ctx	Site	Adopted at the hospital center	3x: visits V1, V3, V4
	OPG RANKL	Site	Adopted at the hospital center	2x: visits V1, V4

\*Creatinine clearance (CC) is calculated by **Cockcroft-Gault** equation on visits V0 and V3:

$$\text{CrCl} = (140 - \text{age}) \times \text{IBW} / (\text{Scr} \times 0,792) \quad (\times 0.85 \text{ for females})$$

If creatinine was measured in mg/dl, to convert the value to mkmol/L it should be multiplied by 88.4.

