#### **4.5 Study withdrawal criteria**

A patient may be withdrawn from the study before the treatment is started, if the investigator discovers deviations from any inclusion criteria, exclusion criteria, or criteria for the treatment initiation. Patients who withdrew before the treatment start (i.e., during screening or washout period), will be substituted with new patients.

In the present study, withdrawal from the study will also mean discontinuation of the investigated treatment.

The patient may be withdrawn from the study due to the following reasons:

1. Withdrawal of the informed consent to participate in the study.
2. Low treatment compliance (<80%).
3. Adverse events that in the investigator's opinion make the treatment continuation impossible, dangerous, or inconsistent with best patient interest and safety. A SAE is not necessarily the cause of early patient withdrawal from the study.
4. According to the investigator, continued participation of the patient in the study threatens the patient's safety.
5. It is necessary to administer treatment prohibited by the study protocol.
6. Failure of the investigated treatment (i.e., recurrent rise of blood pressure  $\geq 180/120$  mmHg after previously achieved target BP level).
7. Death of the patient.
8. Sponsor decision.

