#### **4.6 Early withdrawal procedures**

All patients who were withdrawn from the study early are asked to complete the final visit procedures, if possible. If the decision to terminate the patient participation was made between two scheduled visits, the patient is asked to come for the upcoming scheduled visit, as usual, or make an unscheduled visit.

The reason for the early withdrawal should be indicated in the source documents. If the patient is lost to follow-up, the investigator should make all reasonable efforts to contact the

patient to obtain information on date of withdrawal and reason for the investigated product discontinuation. If the patient cannot be reached, she will be considered as lost to follow-up.

In the case of early investigated product discontinuation due to an adverse event (regardless of whether the event should be immediately reported), the researcher must make every effort to collect information regarding the AE outcome. This information is added to the source documents and CRF, under adverse events section.

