**5.3 Investigated treatment withdrawal**

If the investigated treatment should be withdrawn for any reason before the end of the study, gradual investigated products doses reduction is not required. The early treatment withdrawal means the patient is withdrawn from the study.

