#### **Patient population for statistical analysis**

The following patient populations will be used for the statistical analysis:

**Intention-to-treat population (ITT):** all enrolled patients with investigations data from visits V3 or V4, excluding the enrollment visit.

**Per protocol patient population (PP):** patients who completed the study according to the protocol.

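### Section 7.2 and the visit schedule disagree on when safety chemistry is drawn, so a patient who stops early may leave without an exit panel

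*Combined protocol and SAP*

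**What the plan says.** Five safety tests are at issue: creatinine (with calculated clearance), potassium, sodium, ALT and AST. Their timing is stated in five places.

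- **7.2 Methods and timing:** "Fasting blood samples will be obtained at screening and at the final visit".
- **3.4 Schedule:** the five tests are marked at screening (V0) and Visit 3, and not at Visit 4.
- **3.6.5 Visit 3:** "Fasting blood sampling will be carried out for the following tests: BMP (potassium, sodium, creatinine, total calcium, inorganic phosphorus, ALT, AST" and so on.
- **3.7, Table 2 (laboratory testing):** "2x: visits V0 and V3" for the full chemistry. The footnote calculates creatinine clearance at the same two visits.
- **3.6.6 Final visit:** "Patient's biochemical blood analysis (total calcium, inorganic phosphorus) is performed". None of the five tests is listed.

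Three sections govern what happens when a patient stops. Section 5.3 says "The early treatment withdrawal means the patient is withdrawn from the study", and 4.5 states the converse: "In the present study, withdrawal from the study will also mean discontinuation of the investigated treatment". Section 4.6 then says "All patients who were withdrawn from the study early are asked to complete the final visit procedures, if possible". If the decision falls between two visits, 4.6 asks her to attend the next scheduled visit or an unscheduled one.

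**The concern.** For completers the conflict only moves the second sample between week 24 and week 48. For early leavers it decides whether there is an exit sample at all. Leaving treatment means leaving the study, and the exit visit is defined by reference to the final visit procedures. Whether those include safety chemistry depends on which section the site follows.

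Patients who leave early include those stopped for an adverse event (4.5, reason 3) and those withdrawn at Visit 2 because BP is 180/120 mmHg or higher (5.1). Perindopril can be added at week 4 (3.6.3, 5.1) or week 8 (3.1, 3.8.3.1). A patient could therefore start an ACE inhibitor and stop before week 24 with no scheduled potassium or creatinine in between. At stake is patient safety monitoring, and some completeness of the safety data. The primary comparison is not involved.

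**Working it through.** The plan gives no figure to reproduce on this point. The check sets the sections side by side.

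**Step 1: can the statements be reconciled?** Section 7.2 could be read as adding a final-visit sample to the Visit 3 one. The laboratory table rules that out, because it counts two samples and names both visits. Section 7.2 does not mention Visit 3, and 3.6.6 does not mention the five tests. The conflict is in the current text.

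**Step 2: which reading would be followed?** Most likely the schedule. Sections 3.4, 3.6.5, 3.6.6 and 3.7 agree with each other, and 7.1 itself refers to Table 2 for the safety parameters. Section 7.2 stands alone.

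**Step 3: consequences by time of stopping.** Visit 2 has no blood draw (3.4, 3.6.4).

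| Patient | Schedule followed | 7.2 followed |
|---|---|---|
| Stops at or before Visit 2 (week 8) | Screening only | Screening and exit visit, if held |
| Stops between Visits 2 and 3 | Screening, plus Visit 3 only if she attends after stopping | Screening and exit visit, if held |
| Stops between Visits 3 and 4 | Screening and Visit 3; nothing at exit | Screening and exit visit, if held |
| Completes | Screening and Visit 3; nothing at week 48 | Screening and week 48; nothing at week 24 |

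In the first row, the next scheduled visit for a patient who stops before week 8 is Visit 2, where no blood is taken. The final-visit list, as 3.6.6 has it, lacks the five tests. Only 7.2 gives her a sample.

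In the second row, 4.6 allows her to attend Visit 3, where the panel is drawn. It also allows an unscheduled visit, whose content is not stated.

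**Step 4: the gaps.**

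- Stop just after Visit 2, sample at Visit 3: up to 24 − 8 = 16 weeks off drug, ignoring the ±5-day visit window.
- Patients continuing beyond Visit 3, schedule followed: 48 − 24 = 24 weeks of treatment with no scheduled safety chemistry.

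**Step 5: is blood drawn anyway?** Yes. The final visit already takes blood for calcium, phosphorus, osteocalcin, CTX, OPG, RANKL and telomerase (3.6.6), and an early leaver who completes those procedures gives the same samples. The five tests need no extra visit or venepuncture where those procedures are done.

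**The case against.** The strongest case on the other side is that little is lost. Adverse events are recorded at every visit, tests can be ordered when an event calls for them, and 4.6 requires the outcome of an adverse event leading to discontinuation to be followed. Those safeguards stand, and they are why the point is minor. They leave the sample to the investigator's discretion, however, and an abnormal potassium or creatinine without symptoms may prompt no test. A later SAP cannot recover blood that was never drawn.

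Three stronger readings are tempting, and the documents do not support them.

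- **That 7.2 is the only source of a sample for everyone who stops before week 24.** This fails for stops between Visits 2 and 3, because 4.6 offers attendance at Visit 3.
- **That the reported laboratory results would be biased by a calculable amount.** Section 10.4 plans adverse event counts and organ-system summaries, with no screening-to-Visit-3 chemistry table. The documents give no withdrawal rate and no rate of abnormal values. If leavers resemble those who stay, there is no bias.
- **That patients who stop early for adverse events would drop out of the safety counts.** The ITT set is "all enrolled patients with investigations data from visits V3 or V4, excluding the enrollment visit" and the per-protocol set requires completion, so a leaver without Visit 3 or 4 data is in neither. But 10.4 assigns safety data to a separately named safety population. That population is not defined in the document. Section 10.1 leaves analysis details to a SAP to be finalised before data lock. Losing these patients would require an analyst to put the ITT set in its place, which nothing in the text directs.

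**Conclusion.** The point holds as a scheduling contradiction with a patient-safety consequence. If the schedule is followed, a patient who stops at or before Visit 2 has no scheduled safety chemistry after screening. One who stops between Visits 2 and 3 has it only if she attends Visit 3 after stopping the drug, and one who stops after Visit 3 has no exit panel. Completers have no scheduled panel in their last 24 weeks of treatment.

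This rests on the judgement that the site would follow the schedule and laboratory table over 7.2. If it followed 7.2, the exit sample would exist and the week-24 check would be in doubt. The number of patients affected cannot be stated, because no withdrawal rate is given. The grade is minor, and the CTX comparison is unaffected under either reading.

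**What to change.** 1. Keep the Visit 3 panel.
2. Add creatinine, potassium, sodium, ALT and AST to the Visit 4 draw in 3.6.6, which 7.2 already implies.
3. In 4.6, require the same panel at the exit visit of any patient withdrawn early, whether that visit is scheduled or unscheduled, drawn as near the last dose as possible.
4. Align 7.2, 3.6.6, the schedule in 3.4 and the laboratory table in 3.7 to one statement: screening, Visit 3, and final or early-exit visit.

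Correcting 7.2 to match the schedule, without step 2, would be the wrong repair. It would remove the only sentence that gives completers a late sample, and patients who stop after Visit 3 an exit sample.

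Cost: at most one additional routine panel per randomised patient, 114 × 1 = 114 panels, on blood draws already planned at Visit 4 or exit, plus short edits to five sections.

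As a drafting note only, the SAP should define the safety population, for example as all randomised patients who took at least one dose.
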